25.0 POWER ANALYSIS AND SAMPLE SIZE DETERMINATION

25.1 Retrospective analysis

In order to assess the change in time to readiness for PACU discharge and postoperative respiratory dysfunction (duration of oxygen saturation below 90%) after the introduction of sugammadex we will construct two models. First, we will utilize propensity score matching (PSM)¹⁴ to adequately risk balance the patients pre/post sugammadex introduction (variables mentioned in section 2.4). We will use the nearest-neighbor PSM approach and start with a caliper of width equal to 0.2 of the standard deviation of the logit of the propensity score (as described by Austin¹⁵). We will assess balance of the covariates pre/post intervention by computing

standardized mean differences (SMD) for each variable and will use the rule of thumb “SMD less than 0.1”¹⁶ to indicate adequate balance. Finally, we will also construct a table of patient characteristics pre/post matching to see how well the algorithm balanced the patients. If individual covariates are not adequately balanced with the default propensity score matching algorithm, we will try different matching parameters until adequate balance is achieved (e.g. change the caliper size for what we consider a match and/or run a more advanced propensity score model including interaction or squared terms).

After adequate balance is observed, we will compare our outcomes of interest between pre/post periods using a linear (or log-linear) model for time to readiness and logistic regression for our binary outcome (postoperative respiratory dysfunction) using the propensity matched dataset. An interrupted time-series (also known as segmented regression) analysis as described by Wagner¹⁷ will be conducted for each outcome to estimate the pre-intervention time trend, immediate impact of intervention (change-point), as well as reliably estimating the slope change after the intervention. All estimates of interest from these models will be summarized with p-values and 95% confidence intervals.

Statistical analyses will be performed using R V3.5.1 (Vienna, AU) using the “*Match*” package for propensity score matching and p-values <0.025 (for our two primary outcomes) will be considered statistically significant utilizing the Bonferroni adjustment (0.05/2).

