At this point, we estimate that the pathway will recommend sugammadex for all patients in the medium or high-risk groups as well as some patients in the low risk group (i.e. those patients requiring deep neuromuscular blockade to facilitate surgical conditions such as robotic procedures, free flap cases and others). Given the large number of patients, Merck would supply one vial of study drug for each patient. Thus the total amount of study drug would be no more than 6,500 patients for the one year intervention time.

Given 1 year of data, we observed an overall average PACU discharge time of 152.54 minutes (SD=623.86). With one year of post-data, we are adequately powered (90%) to pick up a reduction in PACU discharge time as small as 27.04 (two-sample t-test, alpha=0.025). Since the current difference in PACU discharge time between low and high risk groups is 67.52 (subtracting 216.62-149.10, see table), we feel the 27.04 minimally detectable difference gives us a great chance of detecting a meaningful difference.

Given 1 year of data (pre-period), we observed the rate of patients with any time SpO2<90% was 4.6% (574/12,467). With one year of post-data, we are adequately powered (90%) to pick up a reduction in this rate if it decreases to around 3.7% in the post (chi-square test, alpha=0.025). Since the current difference in patients with any time with SpO2<90% between low and high risk patients is 5.2% (subtracting 9.2%-4.0%), we feel the minimally detectable difference of 3.7% (4.6%-3.8%) is feasible.

Table 2.

	suppl O2, mean (SD)	PACU disch. Time, mean (SD)	Reintubation, freq (%)	Unplanned upgrade, freq (%)	SpO2<90%, freq (%)	SpO2<95%, freq (%)
OVERALL(n=13,277)	74.81 (241.82)	152.54 (623.86)	89 (0.7%)	138 (1.0%)	574 (4.6%)	6510 (52.3%)
low (n=9,841)	74.48 (280.55)	149.10 (599.78)	63 (0.6%)	111 (1.1%)	372 (4.0%)	4603 (50.0%)
medium(n=2,997)	74.98 (95.67)	154.43 (536.58)	23 (0.8%)	22 (0.7%)	164 (5.8%)	1658 (58.8%)
high (n=439)	79.54 (88.44)	216.62 (1321.46)	3 (0.7%)	5 (1.1%)	38 (9.2%)	249 (60.9%)
Smallest detectable difference (90% power)	9.61	24.84	0.4%	0.4%	3.8%	50.3%

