- Preexisting respiratory disease: The presence of obstructive or restrictive lung disease as defined based on the structured data in the EMR such as previous PFT results, previous medication and previous diagnoses. For analysis purposes patients will be divided into low, medium and high risk groups based on the extent of their disease.

Statistical Methods:

All analysis will be performed by the study team at UCLA.

Retrospective analysis: In order to assess the change in time to readiness for PACU discharge and postoperative respiratory dysfunction (duration of oxygen saturation below 90%) after the introduction of sugammadex we will construct two models. First, we will utilize propensity score matching (PSM) to adequately risk balance the patients pre/post sugammadex introduction. We will use the nearest-neighbor PSM approach and start with a caliper of width equal to 0.2 of the standard deviation of the logit of the propensity score. We will assess balance of the covariates pre/post intervention by computing standardized mean differences (SMD) for each variable and will use the rule of thumb “SMD less than 0.1” to indicate adequate balance. Finally, we will also construct a table of patient characteristics pre/post matching to see how well the algorithm balanced the patients. After adequate balance is observed, we will compare our outcomes of interest between pre/post periods using a linear (or log-linear) model for time to readiness and logistic regression for our binary outcome (postoperative respiratory dysfunction) using the propensity matched dataset. An interrupted time-series (also known as segmented regression) analysis as described by Wagner will be conducted for each outcome to estimate the pre-intervention time trend, immediate impact of intervention (change-point), as well as reliably estimating the slope change after the intervention. All estimates of interest from these models will be summarized with p-values and 95% confidence intervals.

Statistical analyses will be performed using R V3.5.1 (Vienna, AU) using the “Match” package for propensity score matching and p-values <0.05 will be considered statistically significant.

Prospective analysis: The prospective analysis will largely follow a similar framework however we will focus on the primary and secondary outcomes as described above and will use a one year period prior to implementation as our baseline.

Power/Sample Size:

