Given 1 year of data (pre-period), we observed the rate of patients with any time SpO₂<90% was 4.6% (574/12,467). With one year of post-data, we are adequately powered (90%) to pick up a reduction in this rate if it decreases to around 3.8% in the post (chi-square test, alpha=0.05). Since the current difference in patients with any time with SpO₂<90% between low and high risk patients is 5.2% (subtracting 9.2%-4.0%), we feel the minimally detectable difference of 0.8% (4.6%-3.8%) is feasible.

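### Table 2's row of smallest detectable differences mixes differences with post-period rates, carries alpha 0.05 values for the two primary outcomes, and the accompanying SpO2<90% sentence is wrong arithmetic

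*Combined protocol and SAP*

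**What the plan says.** Protocol Section 26.0, Table 2, ends with a row labelled "Smallest detectable difference (90% power". Its entries are supplemental oxygen 9.61, PACU discharge time 24.84, reintubation 0.4%, unplanned upgrade 0.4%, SpO2<90% 3.8% and SpO2<95% 50.3%.

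The text above the table gives other values for the primary outcomes. PACU time is detectable "as small as 27.04 (two-sample t-test, alpha=0.025", and the SpO2<90% rate is detectable "if it decreases to around 3.7% in the post (chi-square test, alpha=0.025". It then concludes: "we feel the minimally detectable difference of 3.7% (4.6%-3.8%) is feasible".

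Section 25.1 sets the test level: "p-values <0.025 (for our two primary outcomes) will be considered statistically significant utilizing the Bonferroni adjustment (0.05/2". Section 25.2 carries a similar framework into the prospective analysis.

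The SAP differs. Under Statistical Methods it says "p-values <0.05 will be considered statistically significant". Under Power/Sample Size it gives 24.84 min and a post-period rate of about 3.8%, both at alpha 0.05, and concludes: "we feel the minimally detectable difference of 0.8% (4.6%-3.8%) is feasible".

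**The concern.** The row label promises one quantity, but the columns do not all hold it. A value of 50.3% against a 52.3% baseline cannot be a difference. The SAP itself identifies 3.8% as the rate after the intervention. A reader who trusts the label would take 3.8 points as the smallest detectable effect on SpO2<90%, when it is below 1 point.

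The protocol also gives two detectable differences for PACU time within one section, 27.04 and 24.84 min, both labelled 90% power. Only the first matches the level at which the protocol will test.

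Finally, the protocol's concluding sentence on SpO2<90% contains a subtraction that does not give the stated result. It sets that figure beside a 5.2-point gap between risk groups to argue feasibility. At stake is a correct statement of what the study can detect on its two primary outcomes.

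**Working it through.** **Inputs (Section 26.0 and Table 2).** PACU time SD 623.86; supplemental oxygen SD 241.82; overall n = 13,277. SpO2<90% 574/12,467 = 4.604%; SpO2<95% 6,510 events; reintubation 89/13,277 = 0.670%; upgrade 138/13,277 = 1.039%. Power is 90%.

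**Assumptions.** Two-sided tests, which is how the plan's figures reproduce. A post-period of equal size, since Section 26.0 expects roughly the same number. A denominator of 12,467 for SpO2<95%, because the plan prints none for that column.

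**Means.** Detectable difference = SD × √(2/n) × (z(1−α/2) + z(0.90)). The z sums are 3.2415 at 0.05 and 3.5230 at 0.025.

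- PACU time: 623.86 × √(2/13,277) = 7.657. At 0.05, 7.657 × 3.2415 = 24.82 (Table 2 and SAP: 24.84). At 0.025, 7.657 × 3.5230 = 26.97 (protocol text: 27.04).
- Oxygen: 241.82 × √(2/13,277) = 2.968. At 0.05, 9.62 (Table 2: 9.61). At 0.025, 10.46.

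**Proportions.** Chi-square test with pooled variance under the null, solved for the post-period rate that gives 90% power to show a reduction.

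| Column | Table 2 entry | Post rate at 0.05 / 0.025 | Difference in points at 0.05 / 0.025 | What the entry matches |
|---|---|---|---|---|
| SpO2<90% | 3.8% | 3.78% / 3.71% | 0.82 / 0.89 | post rate at 0.05 |
| SpO2<95% | 50.3% | 50.2% / 50.0% | 2.05 / 2.23 | post rate, approximately |
| Reintubation | 0.4% | 0.38% / 0.36% | 0.29 / 0.31 | probably post rate |
| Unplanned upgrade | 0.4% | 0.67% / 0.64% | 0.37 / 0.40 | difference |

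For SpO2<95%, starting from the rounded 52.3% baseline gives a post rate of 50.25% at 0.05, which is closer to the printed 50.3%. For reintubation, 0.4% also fits a detectable increase of 0.37 points at 0.05. A continuity correction changes none of these readings.

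**Power for the printed primary values at alpha 0.025.**

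- PACU time: 24.84/7.657 = 3.244; 3.244 − 2.241 = 1.003; power 84.2%.
- SpO2<90% falling to 3.8%: difference 0.008042, null standard error 0.002541, alternative standard error 0.002541. (0.008042 − 2.241 × 0.002541)/0.002541 = 0.92; power 82.2%.

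**The sentence.** 4.6 − 3.8 = 0.8, not 3.7. The protocol's own post rate at 0.025 gives 4.6 − 3.7 = 0.9, in line with the computed 0.89. The SAP's 0.8 is right at its alpha of 0.05 (computed 0.82).

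**The case against.** The strongest reply is that the calculations are sound and that the prose already states the primary targets correctly at the protocol's alpha: 27.04 min and a fall from 4.6% to about 3.7%. No careful reader would take 50.3% as a difference. That stands. A reader might infer that the study's target effect cannot be recovered from the plan, but the prose contradicts this; the table and one sentence are at fault.

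A reader might also infer that the whole row was computed at the wrong alpha. The documents do not support that. Section 25.1 confines 0.025 to the two primary outcomes. The protocol sets no level for the secondary ones, and the SAP uses 0.05, so 9.61 min and the upgrade entry are not shown to be wrong. Nor do the two 0.4% entries discriminate: the upgrade difference and the reintubation post rate each round to 0.4% at either alpha.

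Reintubation cannot be called a definite error, because 0.4% may be a post rate or a detectable increase. The SAP's SpO2<90% sentence is correct at its own alpha and serves here only as contrast. The row also does not cover every secondary outcome: Section 26.0 says power for best-practice performance could not be modelled.

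None of this rescues the entries for SpO2<90%, SpO2<95% or PACU time, or the 3.7% sentence.

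**Conclusion.** The row is wrong as written in three columns. SpO2<90% shows a post rate of 3.8% where the difference is 0.82 points at alpha 0.05 and 0.89 at 0.025, so read as a difference it is overstated more than fourfold. SpO2<95% shows 50.3% where the difference is about 2.05 points at 0.05. PACU time shows 24.84 min where the protocol's alpha gives 27.0, a shortfall of about 2 min, with power of 84% rather than 90%. The protocol's 3.7% sentence is false arithmetic; the difference is about 0.9 points.

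These sizes rest on two-sided tests and on equal periods of 13,277 (12,467 for SpO2). A reader might go on to infer that the sizing method is invalid. It is not: the plan's figures reproduce closely once each is matched to its alpha and its true meaning. How many patients the prospective period will contribute is a separate question and is not judged here. No endpoint or analysis model changes. The significance level does need reconciling between protocol and SAP, because that conflict is why two sets of primary figures exist.

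**What to change.** - Restate the row as absolute differences in every column, with alpha and n per period printed beside it. If post-period rates are wanted, put them in a separate, labelled row.
- Primary outcomes at 0.025, with 13,277 (12,467 for SpO2) per period: PACU time 27.0 min; SpO2<90% 0.9 points (4.6% to 3.7%).
- Secondary outcomes: state the alpha. At 0.05 the detectable reductions are oxygen 9.6 min, SpO2<95% about 2.05 points, reintubation 0.29 points and unplanned upgrade 0.37 points.
- Correct the protocol sentence to a difference of about 0.9 points (4.6% minus 3.7%).
- Reconcile the SAP's 0.05 with the protocol's 0.025 for the primary outcomes, and carry the chosen level through the SAP's power section.

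The cost is one recalculated row, one sentence and an aligned SAP paragraph. The primary figures in the table become slightly less favourable.

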27.0 EARLY STOPPING RULES

Upon review of occurrence of unanticipated adverse drug effects and/or other harmful events as a direct result of the clinical study procedures, the principal investigators, sponsor, and DSMB may decide to:

1. Terminate the study to safeguard subject safety.
2. Stop the recruitment
3. Continue with the recruitment

28.0 RISK/BENEFIT ASSESSMENT

28.1 Risks

Sugammadex is an FDA approved drug. Adherence to the CDS pathway and administration of sugammadex will be at the discretion of the clinician. Thus, study risks are very limited.

28.2 Benefits

All participants in the study may benefit from additional assessments (e.g., additional bloodwork) obtained as part of study procedures.

29.0 STUDY MANAGEMENT

29.1 Selection and Training of Clinical Investigators

The sponsor will keep on file a list of names of all investigators involved in the study. The study will not use, in any capacity, the services of any person debarred under section 306 of the Federal Food, Drug, and Cosmetic Act in connection with this clinical study.

Sponsor personnel or designee will provide all clinical investigators with training on use of the study drug prior to their participation in the clinical study.

The study staff involved will undergo site initiation and training, which will include:

- Study protocol
- Consenting procedures and Human Subjects Protection
- Directions for use
- Investigator responsibilities, including reporting requirements
- Monitoring and auditing
- eCRF completion guidelines
- EDC system

- Electronic recordkeeping
- Study drug accountability procedures
- Protection of subject confidentiality

New members of the clinical site team may be added from time to time at new or existing sites. New personnel should only start their assignment after receiving adequate training in the clinical investigation requirements and this training shall be documented. The names, initials, signatures, functions, and designated authorizations of new site personnel shall be documented.

29.2 Data Management

29.2.1 Electronic Data Capture (EDC)

All data is extracted from the Perioperative Data Warehouse (PDW), a custom built warehouse that extracts data from the EPIC EHR's Clarity Database. After the extraction the data is cleaned and organized in a way that mirrors clinical concepts and facilitates reporting. For each element in the study, an algorithm is built that extracts the necessary raw clinical data and determines the element of interest. A table of these elements is then stored in the PDW and delivered to the study team on a regular basis.

29.2.2 Data Cleaning

Data from the EHR is cleaned at three levels. First, in extracting the data from the EHR multiple tables are combined and concepts are joined to deal with both missing and duplicate data. Second, upon extraction from the EHR standardized keys are used to unify commonly used values such as lab results, medications, etc. Lastly, each of the final elements used in the study are created from multiple raw data points in order to deal with missing and erroneous data. In particular, decisions are made for sensitivity vs precision in order to ensure optimal data capture

The database will be subject to inspection for omitted data, gross data inconsistencies, and deviations. Any deficiencies or deviations will be reviewed, and any necessary action determined (e.g., data query, communication with the study center).

Intermittent data review will be performed, and any discovered errors will be reported to the study site using the electronic query process (as necessary). The study site will be expected to review and complete the query. The data cleaning cycle will be repeated until all data are considered clean.

29.3 Data Back-up, Confidentiality and Security

All data are stored and maintained on servers operated by the UCLA Health Office of Health Informatics and Analytics (OHIA). These servers are maintained behind the UCLA Health firewall and only accessible via a Citrix environment secured by two factor authentication. Whenever possible data for the study are extracted in a fully deidentified manner and only delivered to the study team via secure methods. All data extracts are logged and audits are periodically performed to ensure compliance.

29.4 Data Safety Monitoring Plan

29.4.1 Protection of Subject Privacy

During the study, all data will be collected only in already existing databases. For analysis and reporting purposes, data will only be extracted in the aggregate or in a de-identified dataset.

29.4.2 Database Protection

The database containing patient data will be housed on an OHIA maintained server and secured with password and two-factor authentication. Retrieval of data for analysis will be performed by informatics personnel not on the study team.

29.4.2 Confidentiality During Adverse Event Reporting

AE reports and annual summaries will not include subject- or group-identifiable material. Each report will only include the identification code.

29.4.3 Data Quality and Management

Data for the study will be obtained by automated extraction from the Perioperative Data Warehouse (PDW), the Department of Anesthesiology's Reporting database. Phenotypes for patient risk factors, compliance with best practice pathways and postoperative outcomes will be created using standardized procedures that have been previously reported in the literature. In order to ensure accuracy a subset of cases will be randomly selected for manual review to ensure data accuracy.

The research pharmacy will maintain records of which patients were administered study drug (a criteria for patient inclusion) and these data will be delivered to the study team as an Excel file. These data will be uploaded into the PDW for cross-referencing with the EHR.

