11.0 STUDY POPULATION

UCLA RRUMC and UCLA Santa Monica patients aged 18 and older who had a general anesthetic with either rocuronium or vecuronium will be considered for inclusion in the study.

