13.0 SUBJECT STATUS

Subjects will be classified as follows depending on their status:

- **Enrolled:** After meeting eligibility and being provided study drug from the OR pharmacy.
- **Withdrawn:** Meeting one of the conditions listed in the subject withdrawal section.
- **Subject completion:** Subjects will be considered to have completed this study upon successful confirmation of drug administration to the patient.

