14.0 SUBJECT RECRUITMENT

During the screening phase, patients aged 18 and older who will have a general anesthetic with either rocuronium or vecuronium and who are considered high risk for postoperative pulmonary complications will be flagged in CareConnect and enrolled in the study. Clinicians will receive an alert identifying the patient as a subject in the study and will remind the clinician to pick up the study drug sugammadex from the pharmacy.

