25.2 Prospective analysis

The prospective analysis will largely follow a similar framework however we will focus on the primary and secondary outcomes as described above and will use a one year period prior to implementation as our baseline.

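### The prospective analysis set is not defined, and the stated 90% power holds only with about 13,200 patients per period, while two sections give a prospective size of about 6,500

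*Combined protocol and SAP*

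**What the plan says.** The whole prospective plan is one sentence, given in protocol 25.2 and repeated in the SAP under Statistical Methods: "The prospective analysis will largely follow a similar framework however we will focus on the primary and secondary outcomes as described above", and it "will use a one year period prior to implementation as our baseline". It names no analysis set.

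Three places say who is in the study:

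- Section 14.0: high-risk patients "will be flagged in CareConnect and enrolled in the study".
- Section 13.0 defines enrolled as "After meeting eligibility and being provided study drug from the OR pharmacy".
- Section 29.4.3: "The research pharmacy will maintain records of which patients were administered study drug (a criteria for patient inclusion". The inclusion list in 12.1 has no such item.

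Other text points to a set defined by period. Section 11.0 says that "patients aged 18 and older who had a general anesthetic with either rocuronium or vecuronium will be considered for inclusion in the study". The framework carried over from 25.1 is that "we will compare our outcomes of interest between pre/post periods". Section 29.4.4 lists eligible patients with and without study drug, for accrual review.

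On size, the synopsis and section 7.0 give about 6,500 prospective patients. Section 26.0 expects the prospective sample to be about the same as the 13,000 of the previous year, and uses 6,500 as a ceiling on drug supply. The parallel SAP sentence prints 6,5000.

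**The concern.** Hypothesis 2 in section 9.0 is about creating and implementing a pathway. Testing it requires comparable patients with the pathway on and off. Section 28.1 states that "Adherence to the CDS pathway and administration of sugammadex will be at the discretion of the clinician". If the post group consists only of patients to whom study drug was provided or given, it is selected on a decision made after the alert. The baseline year has no study drug and no alert, so no equivalent selection can be applied there. Propensity matching on recorded covariates cannot be relied on to remove it. Under the 29.4.3 wording, the sugammadex part of the best-practice secondary objective would also be 100% after go-live by construction.

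The size of the set matters too, because the power statement assumes a full year of all-comers in both periods. An undefined set also leaves room to choose it once outcomes are known.

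**Working it through.** **1. Enrolment text side by side.** Flagged (14.0), provided with study drug (13.0) and given study drug (29.4.3) form successively smaller groups. Sections 14.0 and 13.0 conflict directly on when a patient is enrolled. None of the three sits in an analysis section, and no analysis section selects among them. Section 13.2 adds a further link, since it allows data from discontinued subjects into the primary and secondary analyses without saying which subjects those analyses contain.

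The eligibility lists do not settle the matter. Section 12.1 (item 1) and section 6.0 put surgery at either study hospital among the criteria of which one suffices, so every patient there qualifies. The synopsis uses site only as an exclusion.

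**2. Reproducing the plan's figures.** Inputs from section 26.0 and the SAP: SD 623.86 min and 90% power; 27.04 min at alpha 0.025 (protocol); 24.84 min at alpha 0.05 (SAP). Sidedness is not stated; two-sided is inferred because it alone reproduces the figures.

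n per period = 2 × (k × SD / difference)²

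- Protocol: k = 2.241 + 1.282 = 3.523; n = 2 × (3.523 × 623.86 / 27.04)² = 13,214.
- SAP: k = 1.960 + 1.282 = 3.2415; n = 2 × (3.2415 × 623.86 / 24.84)² = 13,256.

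Both agree with the 13,277 patients in Table 2. Both power statements therefore assume about 13,200 in each period.

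**3. If 6,500 is the analysed prospective size (alpha 0.025).** SE = 623.86 × √(1/n₁ + 1/n₂); detectable difference = 3.523 × SE; power = Φ(27.04/SE − 2.241).

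| Baseline vs post | SE | Detectable at 90% | Power for 27.04 min |
|---|---|---|---|
| 6,500 vs 6,500 | 10.943 | 38.6 min | 59% |
| 13,000 vs 6,500 | 9.477 | 33.4 min | 73% |

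For the SAP version (24.84 min, alpha 0.05), power at 6,500 per period is 62%. The second row sets an unrestricted baseline against a restricted post group. It is shown only because the synopsis gives those two numbers.

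**4. SpO2 below 90%.** Baseline 574/12,467 = 4.604%, falling to the stated 3.7%, alpha 0.025. Power is 91% with 12,467 per period, which reproduces the plan. It is 63% with 6,500 per period and 76–78% with 12,467 vs 6,500 (pooled or unpooled variance).

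**5. Sensitivity to the SD.** Steps 3 and 4 use all-comer values, but Table 2 varies by risk group. Combining its medium and high groups (2,997 + 439 = 3,436), including the spread between their means, gives an SD of about 689 min. Back-calculating denominators from the printed percentages gives an SpO2<90% rate of about 6.2%. Assume that a set of 6,500 is those 3,436 plus 3,064 low-risk patients: the SD is about 648 min, SE = 648 × √(2/6,500) ≈ 11.37, the detectable difference is about 40 min, and power for 27.04 min is about 55%.

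**The case against.** The strongest defence is that a period-based set is the natural reading. Drug receipt is absent from the inclusion list. Section 17.0 collects the flag, the alert, receipt of study drug, enrolment and pathway compliance as separate fields, and the receipt field would be constant in a recipients-only dataset. Section 29.4.4 separates eligibility from receipt, and the framework carried over from 25.1 compares periods. On this reading 6,500 is only the drug supply, about 13,000 patients are analysed, and 27.04 min is correct.

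Much of this stands. A reader might infer that the three enrolment statements are mutually exclusive, or that the plan commits to analysing recipients only. The documents support neither: the sets are nested, and the recipients-only reading rests on a parenthesis about pharmacy records and a definition of subject status.

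The defence does not close the gap. The favoured reading is nowhere stated for the prospective analysis, 29.4.3 says otherwise, and the synopsis and section 7.0 label 6,500 as the sample size rather than a supply limit.

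Two cautions about the arithmetic also stand. The percentages depend on an SD and event rate that would differ in a high-risk set. The plan also allows a log-linear model, for which power calculated in raw minutes may be a poor guide when the SD is about four times the mean.

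**Conclusion.** Two things are established. First, neither 25.2 nor the SAP defines the prospective analysis set, and sections 13.0, 14.0 and 29.4.3 would give different ones. If 13.0 or 29.4.3 were followed, the comparison would no longer test pathway implementation. Second, the documents disagree on the prospective size, and the 90% power statements hold only with about 13,200 patients per period.

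A reader might go further and conclude that the result will be biased, or that the study is underpowered. Neither follows. The documents give no basis for the direction or size of a bias. The power shortfall is conditional: it arises only if about 6,500 prospective patients are analysed, which section 26.0 does not expect. In that case 59% (6,500 per period) and 73% (against 13,000) are illustrations. They assume the all-comer SD, two independent samples and no loss in matching; fewer matched patients would raise the detectable difference.

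This should be settled before analysis, because it fixes the population of the primary comparison and needs only wording.

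**What to change.** - In 25.2 and the SAP, define the primary prospective set as all patients who meet the same clinical criteria, derived from the data warehouse, in both the baseline and the post-go-live year, whether or not study drug was dispensed or given. Do not define it by flag or alert fields, which cannot exist at baseline.
- State that the parenthesis in 29.4.3 is not an analysis criterion, and reconcile 13.0, 13.2, 14.0 and 29.4.3.
- Report study-drug recipients as a secondary as-treated set and as the safety set.
- Reconcile the site item in 12.1 and 6.0 with the synopsis, so that the criteria define the intended cohort.
- Align the synopsis, 7.0, 26.0 and the SAP (including 6,5000) on one expected size. Restate the detectable differences for the matched set, with its own SD and event rate.

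Cost: an amendment with sponsor and IRB approval (section 31.0) and no new patient-level collection, since the risk criteria come from the data warehouse and 29.4.4 already lists eligible patients with and without drug. Eligibility must be rebuilt for the baseline year. Intubation attempts and surgical duration are known only during surgery, so the set will include some patients not flagged beforehand. The estimate will include non-uptake and may be smaller, and the detectable differences become less favourable if the set is below about 13,200 per period.
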